The study will prospectively enroll patients seen at the Pediatric IBD center of the Goryeb Children's Hospital. All pediatric patients diagnosed with IBD will be offered enrollment in the study. Data collection surveys will be initially completed at the time of consent (time 0), start of the yoga (time 1) session, end of the yoga session (time 2) and three months after completion (time 3) to determine if the effects of yoga are lasting. Each patient will serve as their own control with the difference between time of enrollment (time 0)/start of yoga (time 1) and start of yoga (time 1)/end of yoga (end of 2) being compared. Patients will enroll in a twelve class series offered twice a year. The classes will be open to a maximum of ten students and will continue to be offered once a week with encouragement to practice daily at home. Patients will have the option to attend a fall or spring set of classes to increase flexibility and improve enrollment.

Through the entire study period patients will receive standard medical therapy as determined by their specific pediatric gastroenterologist. Clearance by their primary gastroenterologist will be required in the 8 week time period prior to starting yoga to confirm they are healthy enough to start yoga.

Sample Size: Based on what has been determined to be the minimal clinically significant difference¹⁴ of HRQOL using the pedQL survey, we would need 34 patients in total as each patient will serve as their own control. . With a sample size of 34 patients, there will be 80% power to detect a 10-point increase (improvement) in average total PedsQL score (0-100 scale)]. The sample size calculation was based on standard deviation of the total score in the Control group = 15.4, probability of Type I error (alpha) of 0.05, and probability of Type II error (beta) of 0.20. That is, in only 20% of the times we will fail to reject the null hypothesis when it is in fact false; i.e. there is a difference.

Recruitment will be feasible over a two-year study time frame as we care for over 800 active IBD patients in our center.

Inclusion Criteria:

- Both male and female patients with IBD.
- Age 10-17 years
- Not currently practicing specific mind-body techniques (yoga, pranayama, biofeedback, hypnosis, guided imagery)
- Diagnosis of IBD

Exclusion Criteria: Other Chronic systemic disease ex. RA, CF, Celiac. Any chronic neurologic condition.

Yoga Introduction:

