The teacher will present modifications to the routine (such as avoiding inverted poses) for patients who are menstruating or having an active flare of GI symptoms.

Data collection measures :

- Impact III:

This is a validated, disease-specific pediatric questionnaire that measures HRQOL in pediatric IBD¹⁶ patients age 9-17 years. It consists of 35 questions and six domains: IBD symptoms, systemic symptoms, emotional functioning, social functioning, body image, and treatment/interventions. The answers are scored on a 5 point Likert response scale.

- Peds QL:

This is a validated pediatric questionnaire that measures general HRQOL in children ages 8-17 years¹⁴. It consists of 23 questions in areas of social, school, emotional and physical functioning. The answers are scored on a 5 point scale and then reverse scored and linearly transformed to a 0-100 scale.

- General Self-Efficacy Scale:

This is a widely used simple 10 item scale that measures a patient's a general sense of perceived self-efficacy, aiming to predict coping with daily life as well as adaptation after stressful life events¹⁷. It is a measure that has been validated in adolescents age 12 and above.

- PCDAI and PUCAI :

The Pediatric Crohn Disease Activity Index (PCDAI) and Pediatric Ulcerative Colitis Activity Index (PUCAI) are validated disease activity indices that include patient symptoms in the previous seven days, physical exam findings, growth parameters

and laboratory studies¹⁸. The information needed to complete this index will be available through the patient's chart as the data collected is part of routine care.

- Physician Global Assessment :

This is a global assessment is part of routine care and determined by the patient's primary GI doctor. The assessment is a global measure of disease activity with the following five categories: inactive, mild, moderate, severe, NA/unknown.

- Short Crohn Disease Activity Index (SCDAI):

This tool has been validated for use in adult crohn's disease patients but is particularly useful for measurement of short-term disease activity and wellbeing. This data will be collected in the crohn's disease patients and includes liquid stools, well-being and abdominal pain²⁵.

- Medication use data:

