We will record what medications the patient is currently using, including steroids, biologics and immune modulators. The dose of medications will also be recorded in order to determine such information as the total dose of steroids, per patient over the study period.

- Yoga Questionnaire:

The yoga questionnaire will consist of questions about past exercise experience, use of other non-mind/body CAM such as probiotics, herbs and supplements. Post yoga the questionnaire will consist of questions if they plan to continue to practice after the study is complete.

- Follow up questionnaire:

Questionnaire will be sent for those subjects who have completed at least nine classes. The follow up questionnaire consists of 5 questions to evaluate if they are still practicing yoga, any benefit from being in the yoga study, has it helped manage their IBD and would they participate in a follow up yoga study.

In addition to the questionnaire/outcome measure collected at baseline and at the different endpoints (Impact III, peds QL, self efficacy scale, PCDAI, PUCAI), baseline demographic and clinical data will be gathered for each patient in the study. Those include age, gender, race, disease type (crohn's, UC), date of diagnosis, areas of bowel involved, medications and dose of steroids.

V. Planned Data Analysis:

Baseline demographic data will be collected and descriptive statistics will be used to profile the patient population. Clinical factors collected at baseline and post intervention and the differences will be

analyzed between the yoga and control group. Categorical data will be analyzed using chi-square or Fisher's exact tests. The distribution of all continuous data will be examined. For continuous variables whose distributions approximate normality, a t-test will be used for comparisons. When normality assumptions are not satisfied, the non-parametric Mann-Whitney U test will be utilized.

The data from the questionnaires will be collected via REDCap secure access.

Statistical significance is considered at $p < 0.05$. All statistical analyses will be performed using MINITAB 17.

VI. Benefits and Risks:

We anticipate the participants who complete the yoga program will have improved HRQOL and self-efficacy. All participants may experience a personal satisfaction by their contribution to a clinical investigation.

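### The test for the primary quality-of-life score is picked after the data are seen, with no criterion, and the fallback (Mann-Whitney U) neither fits the own-control design nor estimates the mean change used for sizing

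*Combined protocol and SAP*

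**What the plan says.** In Section V (Planned Data Analysis), "The distribution of all continuous data will be examined". A t-test follows where the distribution is close to normal. Where it is not, "When normality assumptions are not satisfied, the non-parametric Mann-Whitney U test will be utilized". No normality test, cut-off or decision-maker is named, and the t-test is not said to be paired. The same section speaks of analysing differences between a yoga group and a control group.

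Section IV (Participants and Enrollment) describes a different structure. There is no separate control group. Each patient is their own control, and the change from enrollment (T0) to start of yoga (T1) is set against the change from T1 to end of yoga (T2).

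The Sample Size paragraph claims "80% power to detect a 10-point increase (improvement) in average total PedsQL score" with 34 patients, using a "standard deviation of the total score in the Control group = 15.4". The PedsQL entry under the data collection measures says that answers are "linearly transformed to a 0-100 scale", so the score is bounded.

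**The concern.** No separate rule exists for the quality-of-life outcome, so the generic rule governs the primary aim. Three things follow.

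- The quantity tested depends on a look at the data. A t-test addresses a difference in mean points, and Mann-Whitney addresses rank order. Only the first corresponds to the 10-point change in average score used for sizing.
- The variable to be inspected is left open. A bounded score can be skewed while the within-patient contrast is nearly symmetric, so two analysts following Section V could end with different tests on the same data.
- The named fallback assumes two independent groups. Here the two sets of values come from the same patients, so its null distribution is wrong.

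**Working it through.** **Inputs from the protocol.** N = 34, difference 10 points, SD 15.4, alpha 0.05, power 0.80, scale 0-100.

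**Assumed, because the protocol does not give them.** Within-patient correlation ρ (0.5 and 0.7 in the simulations), equal variance and equal correlation across T0, T1 and T2, PedsQL mean 70 to 80, beta-shaped scores, and Shapiro-Wilk at 0.05 as the normality check.

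**1. The plan's own figure.** For a within-patient difference with SD 15.4, n = (1.960 + 0.842)² × 15.4² / 10² = 7.85 × 2.3716 = 18.6, so 19 (21 with the t correction). For two independent samples, 2 × 18.6 = 37.2, so 38 per group (39 with t). Neither gives 34. With 34 patients, a two-sided paired t-test has 80% power only if the SD of the analysed difference is about 20.2. That mismatch is a separate matter. What counts here is that the sizing target is a mean.

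**2. Does it matter which variable is inspected?** Simulated trials, n = 34, SD 15.4, 4,000 per scenario:

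| Assumed mean | Normality rejected, raw score | Normality rejected, contrast |
|---|---|---|
| 70 | about 23% | 6-7% |
| 75 | about 48% | 10-11% |
| 80 | about 83% | 17-19% |

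The contrast is (T2 − T1) − (T1 − T0). A second simulation used a normal or left-skewed patient effect, scores clipped to 0-100 and a mean of 70. With the skewed effect and no change, the raw-score check rejected in 33% (ρ = 0.5) to 53% (ρ = 0.7) of trials, against 4-5% for a check on the single T1-to-T2 difference.

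**3. Fallback applied to the two successive changes.** Let D1 = T1 − T0 and D2 = T2 − T1.

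- Var(D1) = Var(D2) = 2σ²(1 − ρ).
- Cov(D1, D2) = −σ²(1 − ρ), because T1 enters both with opposite sign.
- True Var(D2 − D1) = 6σ²(1 − ρ). An independent-samples analysis takes it to be 4σ²(1 − ρ).
- The nominal 1.96 therefore acts as 1.96 × √(4/6) = 1.60, a two-sided error of about 0.11 for a mean-based test.

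Simulated Mann-Whitney error is about 10%, in line with this.

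**4. Fallback applied to T1 versus T2 scores.** True variance of the difference is 2σ²(1 − ρ), taken as 2σ². The effective critical value is 1.96/√(1 − ρ): 2.77 at ρ = 0.5 (error 0.006) and 3.58 at ρ = 0.7 (error 0.0003). Simulated Mann-Whitney error is 0.001-0.008. For a 10-point shift at ρ = 0.5, simulated power is about 0.95 for paired t, 0.94 for signed-rank, 0.79-0.81 for Mann-Whitney, and 0.89-0.91 for a raw-score check that switches from paired t to Mann-Whitney.

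**5. Error of the whole rule on the successive changes, if its t-test is paired.** If the switch occurs in a share p of trials, the error is roughly 0.05(1 − p) + 0.10p.

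- Raw scores checked: p = 0.23 gives 0.062 and p = 0.83 gives 0.092. Direct simulation gives 6-9%.
- Contrast checked: p = 0.06 gives 0.053 and p = 0.19 gives 0.060.

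**6. Switching with a paired fallback.** Choosing between paired t and signed-rank by a normality check gives an error of about 4.4-5.5%. The t-test on the contrast, used throughout, gives 4.4-5.2%.

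**The case against.** Three stronger readings are tempting, and the documents support none of them.

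- A reader might infer that raw scores are checked instead of differences. Section V does not say so. It refers to all continuous data and also mentions differences, which are themselves continuous. The high raw-score rejection rates therefore show what the silence permits, and they do not describe what the plan prescribes.
- A reader might infer that choosing the test after seeing the data inflates the false-positive rate by itself. With a paired fallback it does not (step 6). An error of 5.5-6.7% arises only if the analyst may report whichever of paired t and signed-rank is significant, and Section V does not grant that freedom.
- A reader might take 10 points as a success threshold. It is a sizing figure, and the plan's criterion is p < 0.05. Nothing stops the investigators from reporting a mean change beside a rank-test p-value.

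It can also be said that the real defect is the missing pairing, and that correcting Mann-Whitney to signed-rank leaves little behind. Much of this stands: the error and most of the power loss come from the unpaired fallback. What remains is that signed-rank does not estimate the mean change either, and the choice of test would still rest on an unstated criterion.

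**Conclusion.** The point holds as a defect of specification with a cheap remedy. The estimand for the primary aim is not fixed, the variable to be checked is not named, and the named fallback is wrong for paired data.

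The direction of the error depends on what is compared. Mann-Whitney is anti-conservative on the two successive changes (about 10%) and very conservative on T1 versus T2 scores (under 1%, with power of about 0.80 against 0.95). If the t-test is paired, the whole rule on the successive changes gives about 5-6% when the contrast is checked and 6-9% when raw scores are checked. If the t-test is also run unpaired, step 3 applies to it as well.

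The switching frequencies depend on the assumed mean, score shape and normality check. The variance arithmetic in steps 3 and 4 depends only on equal variances and correlations. The mismatch between Mann-Whitney and an own-control design needs no assumption.

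**What to change.** In Section V, replace the generic rule for the primary outcome with one analysis fixed in advance: a paired (one-sample) t-test of the mean within-patient contrast in PedsQL total, that is, the T1-to-T2 change minus the T0-to-T1 change. Report the estimate, 95% CI and p-value whatever the shape of the raw scores. Inspect only the contrasts, and only for gross outliers. Report Wilcoxon signed-rank, not Mann-Whitney, as a sensitivity analysis. Interpret the estimate and CI alongside the 10-point difference used for sizing.

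The cost is about one sentence, with no extra data or patients, and slightly less robustness to extreme outliers, which the sensitivity analysis covers.

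Naming the contrast also exposes its precision. Its SD is 15.4 × √(6(1 − ρ)), which is 26.7 at ρ = 0.5 and 20.7 at ρ = 0.7. Power at 34 patients is then about 0.56 and 0.78. That follows from the comparison Section IV already sets out and not from the choice of test, but the sample-size paragraph should state the SD of the contrast it relies on.

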The role that stress may play in triggering flares of IBD has been investigated in the adult IBD population. Stress has been shown to alter gut permeability and cause the release of neuropeptides with immune modulatory effects⁶. Although some studies suggest conflicting results, several prospective studies have found a positive association with stress and IBD flares, particularly the perception of stressful events, as opposed to discrete events⁶.

Complementary and alternative medicine (CAM) use in pediatric IBD patients ranges from 40-50%⁷⁻¹⁰. Heuschkel et al reported that 41% of IBD patients used CAM because of adverse effects from conventional medications and 59% of respondents not using CAM were interested in learning more about it⁹. In a similar study by Day et al, 72% of children with IBD were noted to have tried CAM therapies, often due to parental frustration with managing their child's illness. Use of CAM was increased particularly in patients with worse QOL^{8, 11}. Mind-Body CAM techniques, especially relaxation, meditation and prayer are popularly used by adolescents with IBD and patients with more severe disease are more willing to consider relaxation strategies¹¹.

Yoga is a mind-body practice that originated in India more than 2000 years ago and is used by greater than a million children in the United States¹². Rates of yoga use in pediatric IBD patients are low^{8, 11}, with one study reporting only 1.4 % use⁸. This presents an opportunity to explore this underused CAM modality in pediatric IBD. Yoga may be well suited as an adjunct to conventional IBD therapy to decrease stress, provide a greater sense of bodily control, and improve HRQOL.

III. Preliminary Studies/Progress Report:

There have not been any studies to date looking at the role of Yoga in IBD. A recent systematic review of the clinical applications of yoga in the pediatric population found 34 studies¹², including a number for psychological health, as well as one for irritable bowel syndrome¹³ which suggested benefit. Unfortunately, many studies suffered from low methodological quality secondary to lack of randomization and inadequate statistical analysis¹².

IV. Research Design and Methods:

Participants and Enrollment:

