We anticipate minimal risk from participation in the yoga program. A systematic review of yoga in the pediatric population found no adverse events reported and suggested that yoga was a low-risk intervention¹². Hatha Iyengar yoga is a very low-intensity physical activity and is less taxing on the cardiovascular system than walking¹⁹. There have been rare case reports of complications following yoga and these were primarily neurologic in origin²⁰⁻²². Patient with any chronic underlying neurologic condition will be excluded. There will be formal "live" instruction to assist in proper technique of the poses.

VIII. Human Subject/Ethical Issues

After the investigators have entered the data from outcome measure questionnaires, all further analysis will be done with "de-identifiable information". All personal identifiers (name, date of birth, medical record number, address etc.) will be removed. Only the previously mentioned investigators will have access to the master list that associates the child's answers to personal information that he or she could be identified with. All data will be kept on a password protected computer database/REDCap secure access. Data will be entered into the database using the alphabetical/numeric codes. A copy of the signed parental permission form will appear in the patient's medical record. The original completed questionnaires will be kept in a locked filing cabinet in the principal investigator's office. The identity of the subjects will not be disclosed in any publication related to this study.

IX. Data Safety Monitoring Plan

The principal investigator (PI) will oversee and assume responsibility for subject safety monitoring. Data monitoring will be the responsibility of the PI in conjunction with the other investigators. A staff member during the course of the study will follow the progress of the study and data entry, to assure utmost accuracy of the data and to detect the possible errors at an early time point. The PI will review all the results. Participant safety data that will be monitored include any adverse experiences, although this is unlikely given the nature of yoga as discussed above.

BIBLIOGRAPHY

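### Adverse experiences are to be monitored, but no described measure prompts for them and reports to the yoga teacher have no stated recording route, so injuries and neurologic events would be caught only passively

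*Combined protocol and SAP*

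**What the plan says.** Section IX (Data Safety Monitoring Plan) assigns responsibility: "The principal investigator (PI) will oversee and assume responsibility for subject safety monitoring". It then names the safety data: "Participant safety data that will be monitored include any adverse experiences, although this is unlikely given the nature of yoga as discussed above". It gives no definition, form, schedule or reporting route. It also provides for a staff member who follows study progress and checks data entry.

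Section IV (Data collection measures) describes Impact III, PedsQL, the General Self-Efficacy Scale, PCDAI and PUCAI, the physician global assessment, SCDAI for the Crohn's patients, medication use, a yoga questionnaire and a follow-up questionnaire. The set collected at baseline and at the endpoints is summarised as "Impact III, peds QL, self efficacy scale, PCDAI, PUCAI".

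Two forms concern the yoga itself. For the yoga questionnaire: "Post yoga the questionnaire will consist of questions if they plan to continue to practice after the study is complete". For the follow-up questionnaire: "The follow up questionnaire consists of 5 questions to evaluate if they are still practicing yoga, any benefit from being in the yoga study". The latter also covers help with managing IBD and willingness to join another yoga study. Its distribution is limited: "Questionnaire will be sent for those subjects who have completed at least nine classes".

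Under Modifications to Routine, patients are told to let the teacher know about symptoms such as dizziness, vomiting, severe pain or bleeding, and about a recent neck or back injury. The teacher may then adapt the class or keep the child out that day.

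Section VI (Benefits and Risks) expects minimal risk and mentions rare complications, mainly neurologic. Section V (Planned Data Analysis) names no adverse-event summary.

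**The concern.** The protocol commits to monitoring harm in minors but describes no step that would find it. The measures that prompt patients cover quality of life, self-efficacy, IBD symptoms, plans to continue and perceived benefit. A strained neck, numbness after a pose or an unplanned medical visit would enter the data only if a family raised it and someone chose to record it.

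Events missed in this way cannot be recovered later. If the trial ended with no adverse events on file, a reader could not tell how far that reflected safety and how far it reflected passive collection. The primary comparison is not at stake. What is at stake is whether the Section IX commitment can be met, and how a low or zero count could be read.

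**Working it through.** **Step 1. Set each source of information against the kind of event it could show.** All sources are in Section IV unless noted.

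| Source | Could show | Would not identify |
|---|---|---|
| Impact III, PedsQL | Worse IBD or systemic symptoms, worse physical functioning | A specific injury or its cause |
| PCDAI/PUCAI, SCDAI, physician global assessment | IBD flare | Musculoskeletal or neurologic events as such |
| Medication record | Steroid or other treatment changes | Events that lead to no recorded medication |
| Yoga questionnaire, post-yoga part | Plans to continue | Harm (not a named topic) |
| Follow-up questionnaire | Continued practice, benefit, help with IBD, interest in another study | Harm (not a named topic); anyone with fewer than nine of the twelve classes |
| Report to the teacher at class | Symptoms or recent injury on that day | Nothing says that it is recorded or reaches the principal investigator |
| Staff member (Section IX) | Data-entry errors | Events never entered |

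**Step 2. Timing.** Surveys fall at times 0, 1, 2 and 3. PCDAI and PUCAI use symptoms from the previous seven days. The class series lasts 12 weeks, or 12 × 7 = 84 days, so an index completed at time 2 looks back over 7/84, about 8%, of the yoga period. A problem that began and cleared mid-series could leave no trace. Daily home practice is also encouraged, with no teacher present.

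**Step 3. What zero events in 34 patients would mean.** The protocol gives no adverse-event figure to reproduce. The only input is the planned sample size, n = 34, assuming that all are enrolled and followed.

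- One-sided 95% upper limit: solve (1 − p)^34 = 0.05, so p = 1 − 0.05^(1/34) = 0.0843, or 8.4%.
- Upper end of the two-sided 95% interval: p = 1 − 0.025^(1/34) = 0.1028, or 10.3%.

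Both refer to the risk of at least one event per patient, and both require complete capture.

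**Step 4. Sensitivity to capture.** Let q be the fraction of affected patients whose event is recorded. The data then bound p × q, so the one-sided limit on p is 0.0843/q. The chance of recording zero is (1 − p × q)^34. The values of q and p are assumptions, used only to show how strongly the reading depends on them.

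| Assumed q | Limit on p after 0/34 | P(zero recorded) if p = 5% | P(zero recorded) if p = 10% |
|---|---|---|---|
| 100% | 8.4% | 17.5% | 2.8% |
| 75% | 11.2% | 27.3% | 7.1% |
| 50% | 16.9% | 42.3% | 17.5% |
| 25% | 33.7% | 65.2% | 42.3% |

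Only the limit in the first row follows from the protocol's own number.

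**The case against.** The strongest reply is that much harm would be seen anyway, and that no safety claim is planned. Several parts of this stand.

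- **Flares.** The disease-activity and quality-of-life measures would show many of them without anyone volunteering. It would be wrong to say that the trial captures only what families report.
- **Patients are told to speak up.** The advice to inform the teacher covers dizziness and neck or back injury, which bear on the neurologic risk in Section VI. The defect is that no recording or onward route is described.
- **The follow-up form is not solely about benefit.** It also covers continued practice and joining another study, and four topics are named for five questions. Benefit and help with IBD are the only effects named. Even if the remaining question asked about harm, the nine-class rule would still restrict who answers it.
- **No safety endpoint exists.** The aims in Section I are quality of life and self-efficacy, and no conclusion of no adverse events is announced. A reader might infer that the trial's benefit-risk statement is biased; the documents contain no such result, so that goes too far.

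A reader might also use Section III to undercut the expectation of low risk. Section VI cites a review: "A systematic review of yoga in the pediatric population found no adverse events reported and suggested that yoga was a low-risk intervention". Section III says of that review: "Unfortunately, many studies suffered from low methodological quality secondary to lack of randomization and inadequate statistical analysis". The faults named there are randomization and statistics, not the collection of harms, so under-reporting is not shown. The expectation also rests on low physical intensity, rare case reports, the neurologic exclusion and live instruction.

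None of this supplies a prompt for injury or neurologic symptoms, or a path from the teacher to the principal investigator.

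**Conclusion.** The point holds in a limited form and merits a change to the plan. Section IX promises monitoring, but for yoga-related events the described procedures amount to passive capture. The gap is mainly musculoskeletal and neurologic events, events that resolve between surveys, and children who stop before nine classes. It is small for IBD flares.

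On size, zero events in 34 patients would exclude a risk above 8.4% (one-sided 95%; 10.3% with a two-sided interval) if capture is complete and all 34 are followed. The larger limits of 11.2% to 33.7% come wholly from assumed capture rates of 75% to 25% and from treating all event types alike. They are an illustration, not an estimate for this trial.

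The conclusion rests on the measures as Section IV describes them. The questionnaires are summarised there rather than reproduced, so an item on harm that is not described cannot be ruled out.

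**What to change.** 1. Add one short adverse-event item to the existing surveys at times 1, 2 and 3, covering the period since the last survey: an open question, plus prompts for injury, neurologic symptoms and unplanned medical visits. Give it to every enrolled patient regardless of classes attended.
2. Have the teacher note any symptom reported at class, and any class missed because of one, and pass the note to the principal investigator. This records what the teacher is told and changes no rule on participation.
3. In Section V, state that events will be reported descriptively for times 0–1, 1–2 and 2–3, with follow-up time for each. The time is needed because the length of the 0–1 interval is not fixed: patients may choose fall or spring classes, so raw counts before and during yoga are not directly comparable.

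The cost is about a minute per survey, a brief teacher note per class, and a few more minor events to report. No visits are added, and the quality-of-life analysis is unaffected.
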